9.4.4 SAFETY ANALYSES

Safety will be analyzed for all Subjects in ITT Population in the three groups. No formal statistical analysis will be performed.

To investigate the safety of Galnobax® vehicle for establishing non-deleterious effects of Vehicle on wound healing, number and percentage of events as well as number and percentage of Subjects with events related to local wound assessment (local pain, edema, erythema) of Target Ulcer in Vehicle plus SoC group will be tabulated and reported.

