^j Subject Education and training on Diabetes management and use of off-loading device will be done as and when required

^k The AE reporting will begin from the application of the first dose of the IP from the Baseline Visit

^l Debridement of ulcer as and when necessary during site visit

^m Nutritional information should be provided to Subject as and when necessary

ⁿ Photographs of both the legs will be taken from various angles to ensure that there are no more than three ulcers on both the legs

^o In case the ulcer/wound closes within 12-weeks of Treatment Phase, the Subject will immediately enter the 12-weeks of Follow-Up Phase. In case of the Subject, whose Target Ulcer reopens during 12-weeks of Treatment Phase (within 84 days from Baseline) which is prior to the confirmation of Target Ulcer closure, the Subject would be given the treatment to complete 12-week of Treatment Phase

^p During Follow-Up Phase, if the Target Ulcer has reopened after confirmation of its closure, the Subject will still be continued with the Follow-up assessment.

^q This window period is from the Screening Visit

^r EOT is at week 12 visit or any visit on which first observation of Target Ulcer closure has happened or treatment is Stopped

^s EOS is at week 24 visit or any visit on which the Subject exits the Study

^t Window period of ±3 days will be allowed for each Treatment visit as well as FU1 and FU2 visits and window period of ±5 will be allowed for FU3 and FU4

Note: *Dispensing of Wound dressing material will be provided as long as required

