2.3 RISK/BENEFIT ASSESSMENT

2.3.1 KNOWN POTENTIAL RISKS

Phase 1/2 study of Galnobax® on 44 DFU Subjects reported the following:

- a. No deaths were reported during the study.
- b. There were 4 SAEs (arthritis bacterial, infected skin ulcer, gastroenteritis, and cellulitis) reported during the study, all in the Galnobax® 20% group and none determined by the Investigator as related to the study drug. All these SAEs were resolved during the study.
- c. There were 29 AEs of which only 2 were determined by the Investigator as related to the Study drug (TEAEs) with 1 Subject each in the Galnobax® 14% [TEAE: skin discoloration] and Galnobax® 20% [TEAE: erythema] groups. Both these events were non-serious and mild in intensity which were reversible on discontinuation of drug. None of the vital signs and Electrocardiogram (ECG) abnormalities were reported as TEAEs.
- d. Furthermore, the drug substance used in Galnobax® (Esmolol hydrochloride) is approved for intravenous application with all reported AEs being mild, transient and reported to be reversible after discontinuation of dosing in spite of systemic concentration of 868-1470 ng/mL²³ and human peak plasma concentration of 500, 1200 and 2500 ng/mL respectively at the infusion rate of 100, 250 and 500 µg/kg/min²². As against this, the clinical pharmacokinetic (PK) studies of Galnobax® conducted as part of the Phase 1/2 study demonstrated that the systemic concentration of its drug substance (Esmolol hydrochloride) through topical administration was below quantification limit (10 ng/mL) at any time during the treatment period, irrespective of wounds of different sizes and doses of Galnobax®. This low systemic absorption and localized action is also substantiated by non-clinical PK studies conducted in Lewis rats and in minipigs.²¹

The non-clinical toxicity studies of Galnobax® showed slight irritation in rabbit model which was found to be reversible and did not elicit skin sensitization in guinea pig model.

All of the above is sufficient to conclude that Galnobax® with no deaths, no SAEs related to the drug, only 2 drug related AEs which were reversible and minimal systemic absorption (way below approved tolerated concentrations) as established in Phase 1/2 study has a favorable human safety profile.²¹

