Treatment Visits V3 to V14 (Week 1 to Week 12, Day 7 to Day 84 [Window period ± 3 days for each scheduled visit])

The Subjects assigned to Galnobax® plus SoC, Vehicle plus SoC or only SoC Group will receive the treatment twice daily from Study Nurse for up to 12-weeks or until complete closure of Target Ulcer, whichever is earlier.

All Subjects will visit the Study site once every week as given in Study calendar. Assessment will be done at various Treatment visits as follows:

- Urine pregnancy test will be performed (as applicable) after every 4 weeks till V14 or EOT, whichever is earlier
- Vital signs (blood pressure, pulse rate, respiratory rate, and temperature)
- Systematic physical examination and body weight after every 4 weeks till V14 or EOT, whichever is earlier
- Laboratory tests (hematology tests and biochemistry) after every 4 weeks till V14 or EOT, whichever is earlier
- HbA1c test at V14 or EOT, whichever is earlier

- Measurement of random blood glucose. If abnormality is observed, the Investigator may recommend pre- and post-prandial blood glucose measurement and modify dose or medication for adequate blood sugar control
- ECG or 2 D echocardiography (2D-ECHO only if ECG is not conclusive) after every 4 weeks till V14 or EOT, whichever is earlier
- X-ray of the foot under the Study will be taken at the Investigator's discretion for ruling out osteomyelitis. Other methods such as bone scan, leukocyte scan or MRI as needed may be used by the Investigator, for confirming the osteomyelitis depending on the Target Ulcer status
- Detail Foot Examination to assess vascular, neurological, dermatological and musculoskeletal signs and symptoms of the foot(s) with Target Ulcer after every 4 weeks till V14 or EOT, whichever is earlier
- Grading and staging of Target Ulcer as per Texas system of wound classification (See *Attachment 1*)
- Local examination and infection status of Target Ulcer for presence of edema, warmth, erythema, pain, scaling, pus, exudates, cellulitis, callus, maceration or swelling and any signs of infection
- Assessment of Target Ulcer characteristics in terms of wound edge, color, drainage amount and type, peri-wound conditions and color and percent wound bed covered by granulation tissue, fibrin slough, and necrotic tissue
- Surgical or Sharp debridement of Target Ulcer, if required along with documentation of type of debridement (e.g. callus removal, sharp or surgical), reason for debridement
- Target Ulcer measurement

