The Subject whose Target Ulcer has closed within 12-week Treatment Phase and has entered the Follow-Up Phase will continue to use protective covering or bandage (if advised by the Investigator) on the Target Ulcer until confirmation of the Target Ulcer closure. If the Target Ulcer remains closed during Closure Confirmation period, then the Target Ulcer will be confirmed to be closed. The time to Target Ulcer closure will be the time from the Baseline Visit when Target Ulcer was first observed closed for which Target Ulcer Closure was confirmed.

During this follow-up phase, if the Target Ulcer reopens during the Closure Confirmation period which lies within 84 ± 3 days from Baseline visit, the Subject would be given the treatment to complete 12-week of Treatment Phase. For example, if the Target Ulcer closes before 8 weeks of treatment and reopens within 4 weeks of Closure Confirmation period, the Subject will restart the treatment and continue only till 12-weeks (84 ± 3 days) of treatment from Baseline visit. On completion of that period, Subject will enter the Follow-Up Phase.

During this follow-up phase, if the Target Ulcer reopens after confirmation of the Target Ulcer closure, the Subject will still be continued with the Follow-up assessment period and further evaluations would be as per Follow-up visit scheduled.

During this 12-week Follow-Up phase (84 ± 5 days from EOT), the closed Target Ulcer will be monitored to distinguish actual healing from transient wound coverage and for AEs, if any.

All Subjects will undergo following assessments during FU1 to FU4 visits

- Sample collection for Urine pregnancy test (as necessary) at FU2
- Vital signs (blood pressure, pulse rate, respiratory rate, and temperature)
- Systematic physical examination and body weight at EOS or FU4, whichever is earlier
- Laboratory tests (hematology tests, biochemistry, and HbA1c) at EOS or FU4, whichever is earlier
- Measurement of random blood glucose. If abnormality is observed, the Investigator may recommend pre- and post-prandial blood glucose measurement and modify dose or medication for adequate blood sugar control
- ECG or 2 D echocardiography (2D-ECHO only if ECG is not conclusive) at FU1
- Subject Diary review will be done by blinded Investigator for all subjects in follow up Phase
- Offloading, dressing compliance

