Approximately 5 mL blood will be collected from each Subject at visits where laboratory assays are to be performed. These visits are Screening visit V1, V6, V10, V14 or EOT visit whichever is earlier and V18 or EOS/FU4 whichever is earlier. The laboratory assessments are haematology, biochemistry and HbA1c. Thus, total volume of blood that will be withdrawn per Subject during the Study will be approximately 25 mL.

Any additional/unscheduled investigation(s) can be done at the Investigator's discretion as needed. These investigations may also be done at local laboratory, if required.

Urine pregnancy test will be done locally in women of child bearing potential at Screening Visit V1, V6, V10, V14 or EOT whichever is earlier, and V16/FU2 at Follow-Up.

ECG and X-ray: ECG will be done at Screening Visit V1, and every 4 weeks after Baseline during Treatment visit V6, V10, and V14 or EOT and V15/FU1 at follow-up. X-ray of the foot under Study will be performed at the Screening Visit and further at the Investigator's discretion to rule out osteomyelitis.

Recording and Assessment of adverse events: if there is any clinically significant abnormality or signs or symptom detected in the Subject or reported by the Subject after the application of treatment, it will be recorded as an adverse event. The AE assessment will be done from Baseline Visit V2 to V18 or EOS/FU4, whichever is earlier.

Assessment of local pain: Local pain at the Target Ulcer site will be measured in terms of 11-point universal pain scale as mentioned in *Attachment 4*.

Assessment of local edema: Local edema at the Target Ulcer site will be measured in terms of 5-point edema scale as mentioned in *Attachment 4*.

Assessment of local erythema: Local erythema at the Target Ulcer site will be measured in terms of 5-point erythema scale as mentioned in *Attachment 4*.

The local pain, edema and erythema will be recorded at all the visits from Baseline Visit V2 to V18 or EOS/FU4, whichever is earlier.

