8.2.3.3 EXPECTEDNESS

Investigator will be responsible for determining whether an adverse event (AE) is expected or unexpected. An AE will be considered unexpected if the nature, severity, or frequency of the event is not consistent with the risk information available for the study intervention. The treatment is being given topically in this Study, therefore the AEs that are expected at and around the Target Ulcer location are: hypersensitivity, irritation, inflammation of ulcer. Since the Target Ulcer is an open wound, possibility of infection at the wound site cannot be ruled out. The infection at Target or non-Target Ulcer will be reported as AE.

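### Local pain, edema and erythema are graded in all three groups, but a table of local-assessment events is specified for the Vehicle group only, with no reference column and no definition of an event

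*Combined protocol and SAP*

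**What the plan says.** Section 8.1 states that "The local pain, edema and erythema will be recorded at all the visits from Baseline Visit V2 to V18 or EOS/FU4, whichever is earlier". Pain is graded 0 to 10, edema and erythema 0 to 4 (Attachment 4). The scoring is not limited to one arm. For the treatment visits, section 8 says "All Subjects will visit the Study site once every week as given in Study calendar", and for follow-up, "All Subjects will undergo following assessments during FU1 to FU4 visits"; the local scales are in both lists of assessments.

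The analysis is limited to one arm. Safety endpoint 2 (synopsis and section 3) is the proportion of subjects in the Vehicle plus SoC group with events on the local wound assessment. Section 9.4.4 matches it: "events related to local wound assessment (local pain, edema, erythema) of Target Ulcer in Vehicle plus SoC group will be tabulated and reported". The only safety endpoint for Galnobax is the proportion of subjects with TEAEs.

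Two other parts of the protocol bear on this. Sections 4.1 and 4.2 say that the Vehicle arm will be evaluated against SoC alone, to see whether the vehicle harms healing. Section 9.2 says that neither testing nor a statistical comparison is planned for the Vehicle arm.

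**The concern.** Galnobax is a topical gel, and local tolerability is an obvious safety question for it. Section 8.2.3.3 says that "the AEs that are expected at and around the Target Ulcer location are: hypersensitivity, irritation, inflammation of ulcer". Both drug-related events in the Phase 1/2 study were local: "1 Subject each in the Galnobax® 14% [TEAE: skin discoloration] and Galnobax® 20% [TEAE: erythema] groups". Graded scores can detect mild irritation that nobody would report as an adverse event. Followed as written, section 9.4.4 uses them only in the smallest arm, and that arm does not receive the drug.

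The Vehicle table also fails its own purpose. An open ulcer can be painful, swollen or red whatever is put on it. A percentage from one arm, with no SoC column beside it, cannot separate an effect of the vehicle from the ordinary state of the ulcer.

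**Working it through.** The documents give no figure for local tolerability, so there is none to reproduce. The check has four steps.

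**1. How often the scales are scored.** V2 to V14 is 13 visits and FU1 to FU4 is 4, so 13 + 4 = 17. This is a scheduled maximum, and it includes Baseline. The Schedule of Activities says "In case the ulcer/wound closes within 12-weeks of Treatment Phase, the Subject will immediately enter the 12-weeks of Follow-Up Phase". A subject whose ulcer first closes at week 4 and stays closed is scored at V2 to V6 and four follow-up visits, 5 + 4 = 9. With closure at week 8 the count is 9 + 4 = 13. On treatment after Baseline, the maximum is 12 visits (V3 to V14).

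**2. Where the data go.**

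| Group | Scales scored | Table of local-assessment events | Local reactions reported as AEs |
|---|---|---|---|
| Galnobax + SoC | yes | none specified | TEAE tables |
| SoC | yes | none specified | TEAE tables |
| Vehicle + SoC | yes | yes (9.4.4) | TEAE tables |

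The TEAE route depends on reporting. Section 8.1 makes a sign or symptom an AE if it is clinically significant. Section 8.2.5 makes out-of-range laboratory, vital-sign and ECG changes AEs whatever the Investigator thinks of their significance, but sets no such rule for the local scores. Section 8.2.5 also counts worsening of the ulcer as an AE, while section 8.2.7 lets the Investigator leave out progression of the underlying disease. No section says which score, or change in score, is an event for endpoint 2.

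**3. Share of subjects outside the table.** Allocation of 350 subjects in the ratio 3:3:1 gives 150, 150 and 50. Outside the table: (150 + 150)/350 = 300/350 = 86%. If the comparison in sections 4.1 and 4.2 is carried out on these scores, the SoC group is used too, and the share is 150/350 = 43%. These are full-enrolment counts, before untreated subjects are excluded.

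**4. What a three-group table would give.** The 95% half-width for a difference, with a common rate p, is 1.96 × √[p(1 − p)(1/n₁ + 1/n₂)]. The documents give no p, so a range is assumed.

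| Assumed p | Galnobax vs SoC (150 vs 150) | Galnobax vs Vehicle, or Vehicle vs SoC (150 vs 50) |
|---|---|---|
| 5% | 4.9 points | 7.0 points |
| 10% | 6.8 points | 9.6 points |
| 20% | 9.1 points | 12.8 points |

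For p = 10%: 1.96 × √(2 × 0.09/150) = 0.068, and 1.96 × √(0.09/150 + 0.09/50) = 0.096.

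For contrast, 5 events in 50 Vehicle subjects gives 10% with an exact 95% CI of 3.3% to 21.8% and nothing beside it. With no events at all, the one-sided 95% upper bound, 1 − 0.05^(1/n), is 5.8% for n = 50 and 2.0% for n = 150.

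**The case against.** The strongest reply is that local safety of Galnobax is analysed. Section 9.4.4 covers all three groups. Section 8.2.4 captures local reactions as AEs, and section 9.4.4.1 tabulates TEAEs by preferred term and system organ class, with summaries by severity and relationship. Its TEAE definition includes worsening of something already present. This stands. A reader might infer that local tolerability of the drug goes unanalysed, or that the trial could say nothing about irritation. The documents do not support either reading: reported irritation, erythema or pain will appear by group. What may be lost is low-grade change that no one reports.

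A reader might also infer that a three-group score table would capture the kind of event seen with the 14% gel in Phase 1/2. It would not. That event was skin discoloration, which none of the three scales grades; the erythema event was in the 20% group, a strength not studied here. The Phase 1/2 events show that local reactions matter, and no more.

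Section 9.4.1 has a general rule to summarise data by treatment group, and section 9.4.12 promises listings of key variables. Neither names the local scores. Laboratory tests, vital signs and physical examination each have their own analysis text, whereas the text on the local scales names one arm. A programmer following section 9.4.4 would produce a Vehicle-only table.

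Section 9.4.1 also announces a separate SAP, which is not among the documents reviewed. It may add tables by group, and this cannot be checked. But endpoint 2 is itself limited to Vehicle, so the protocol wording needs correcting in any case.

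Lastly, section 9.2 can be read as ruling out only formal inference, which leaves room for a descriptive comparison. That reading would reconcile it with sections 4.1 and 4.2, but section 9.4.4 still supplies no SoC column.

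**Conclusion.** The point holds as a gap in what is specified. The graded local scores have a dedicated endpoint and table in one of three groups, at most 50 of 350 subjects. For Galnobax and SoC, only AE-reported local reactions are sure to be tabulated. With no definition of an event, even the Vehicle table can be built in more than one way. Without a reference column it cannot support a claim that the vehicle does no harm, and it does not deliver the comparison with SoC that sections 4.1 and 4.2 describe.

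The 86% share assumes full 3:3:1 enrolment and section 9.4.4 followed literally. The half-widths (6.8 and 9.6 points at 10%) rest on an assumed rate; they show what precision is available and do not measure an error in the plan. The primary efficacy analysis is not affected. The change is worth making because the data are already collected.

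**What to change.** - In safety endpoint 2 and section 9.4.4, tabulate pain, edema and erythema side by side for all three groups, by visit and as the proportion of subjects with an event. The by-visit table is needed because early closers have fewer visits at which an event can be seen.
- Define an event in advance as worsening from the subject's own Baseline score. The sponsor should set the cut-off for each scale and the visits that count.
- Show differences with 95% CIs for Galnobax vs SoC, Galnobax vs Vehicle and Vehicle vs SoC, labelled descriptive and without formal testing.
- Reconcile sections 4.1 and 4.2 with sections 9.2 and 9.4.4 on whether, and how, Vehicle is compared with SoC.
- Carry the same definitions into the separate SAP.

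The cost is protocol and SAP wording and one more descriptive table. No new data, visits or hypothesis tests are needed.
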